4.10.3. Adverse Events of Special Interest

The following events are considered AE of special interest and will be summarized:

- Platelet count reduction to levels below 50,000/mm³ accompanied by a major bleeding event (MB) or clinically relevant non-major bleeding (CRNMB) event or platelet count reduction to levels below 25,000/mm³, irrespective of bleeding status
- Requirement of any use of medications (such as antihistamines, acetaminophen, non-steroidal anti-inflammatory drugs [NSAIDs], corticosteroids, etc.) as pre-treatment to avoid a hypersensitivity reaction or recurrence of a previous hypersensitivity reaction.

The number and percentage of patients experiencing events as well as the total number of reported events, classified by SOC and PT, will be tabulated by treatment group.

The following additional analyses may be provided if supported by data:

- A cumulative incidence plot
- Risk difference and its 95% CI in the crude incidence rates between each active treatment group (or total ISIS 678354) and pooled placebo group. The analysis methods are detailed in Section 4.10 of this SAP.
- Exposure adjusted incidence rates (EAIRs) and risk difference (or ratio) in EAIRs may also be provided, if deemed necessary. EAIR is defined as the number of patients who experienced at least one event times 100 divided by total patient-years at risk for the event. For patients with events, the time at risk is the time from the first dose date to the first onset of an event (i.e., first event date minus first dose date plus one day divided by 365.25); for patients with no event, the time at risk is the total duration in the on-study period (i.e., last participation date minus first dose date plus one day divided by 365.25).
- Exposure adjusted event rates (EAERs), defined as the number of events times 100 divided by the total duration in the on-study period in year.

4.10.4. Other Events of Interest

4.10.4.1. Local Cutaneous Reactions at the Injection Site

Local cutaneous reaction at injection site (LCRIS) is defined as (A) moderate or severe adverse events with the preferred terms (PTs) including Injection site erythema, Injection site swelling, Injection site pruritus, or Injection site pain that started on the day of injection, persisted for at least two days (i.e., event onset date on the day of injection and resolution date not on the day of injection or the day after injection) or ongoing; or (B) any AE at the Study Drug injection site, regardless of severity, that leads to discontinuation of study drug, where AE at the Study Drug injection site is the principal reason for discontinuation. LCRIS will be summarized using the MedDRA coding system, by PT and by treatment group. Patients with moderate, severe and any LCRIS will also be summarized. Discontinuations due to AE at the injection site will be summarized separately.

Percentage of injections leading to LCRIS will be summarized by PT and overall using the descriptive statistics. Additionally, percentage of injections leading to events will be summarized by moderate, severe severity and overall discontinuation of Study Drug due to AE at injection site.

Percentage of injections leading to LCRIS will be calculated as follows for each patient: (A/B)*100, where A = number of injections with a LCRIS, and B = total number of injections. Doses that are split across multiple injections are counted as a single injection.

The duration to resolution of a LCRIS will be summarized descriptively by treatment group and total ISIS 678354 treated. If there are multiple LCRIS related to an injection and no overlap between events, the duration will be calculated as the sum of the duration of all LCRIS that are related to the injection. If there are overlaps, the duration will be calculated using the earliest start date and latest stop date of all LCRIS that are related to the injection. For unresolved LCRIS with missing stop date, the last participation date will be used in the calculation.

In addition, for patients who experienced LCRIS, time to onset of the first event, the number of injections prior to the first LCRIS will also be summarized descriptively by treatment group and total ISIS 678354 treated.

LCRIS will also be listed.

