9.4.3.5. Outcome of the Adverse Event

If the event is a non-serious AE, then the event's outcome is characterized by 1 of the following:

- **AE Persists:** Patient terminates from the trial and the AE continues
- **Recovered:** Patient recovered completely from the AE
- **Became Serious:** The event became serious (the date that the event became serious should be recorded as the Resolution Date of that AE and the Onset Date of the corresponding SAE)
- Change in Severity (if applicable): AE severity changed

If the event is an SAE, then the event's outcome is characterized by 1 of the following:

- **Ongoing:** SAE continuing
- **Persists (as non-serious AE):** Patient has not fully recovered but the event no longer meets serious criteria and should be captured as an AE on the non-serious AE eCRF (the SAE resolution date should be entered as the date of onset of that AE)
- **Recovered:** Patient recovered completely from the SAE (the date of recovery should be entered as the SAE resolution date)
- **Recovered with Sequelae:** The signs/symptoms of the reported SAE have improved but not completely resolved, and a new baseline for the patient is established since full recovery is not expected
- **Fatal:** Patient died (the date of death should be entered as the SAE resolution date)
- Unknown: The outcome of the reported SAE is not available, e.g., patient is lost to follow-up

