4.10.2. Adverse Events

All adverse events will be coded by the MedDRA coding system. The final version used will be designated in the clinical study report.

The following imputation rules will be applied to impute start dates under conservative principles:

- If year, month and day are all missing then assign the date of first dose of Study Drug.
- If month and day are missing and year is:
 - the same as the year of the first dose of Study Drug then assign the month-day of first Study Drug
 - o earlier than the year of the first dose of Study Drug then assign December 31
 - \circ after the year of the first dose of Study Drug then assign January 1
- If only day is missing and month-year is:
 - the same as the month-year of the first dose of Study Drug then assign the day of first Study Drug
 - $\circ~$ earlier than the month-year of the first dose of Study Drug then assign the last day of the month
 - $\circ~$ after the month-year of the first dose of Study Drug then assign the first day of the month

Imputation will be performed for the end date only if the day or month is missing (i.e., year is present) for a resolved AE as follows:

- If month and day are missing and year is:
 - the same as the year of the last dose of Study Drug then assign the month-day of the last dose of Study Drug
 - o otherwise, assign December 31
- If only day is missing then assign the last day of the month

If the imputed start date is later than the imputed end date then set the imputed start date to the imputed end date.

An adverse event will be regarded as treatment emergent if it is present prior to receiving the first dose of study drug and subsequently worsens, or is not present prior to receiving the first dose of study drug but subsequently appears.

In addition, if the severity of an AE changes during the study, a separate AE will be recorded for each severity on the AE CRF. The "first" and "second" AE records will be identified based on the AE start date. AE start date of the second record will be the AE stop date of first record. These linked events should be compared pairwise. Consider the following two cases, where the AE severity (mild/moderate/severe) and seriousness (Yes/No) between the two records in a pair are compared.

Case 1: The first AE record in the pair occurs before the first dosing, and the second AE record occurs after the first dosing.

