If the AE severity or seriousness of the second record is worse than that of the first record, then only the second AE is deemed as a TEAE. Otherwise, neither record is considered as TEAE.

Case 2: Both AE records in the pair occur after first dosing.

The worst AE is considered as a TEAE.

- The frequency of patients with any incidence of AEs and the number events will be summarized by MedDRA preferred term and system organ class for:
- Any TEAE
- TEAEs potentially related to Study Drug. Related is defined as "Related", "Possible", or missing relationship to Study Drug
- Any treatment-emergent adverse event by severity. At each level of patient summarization, a patient is classified according to the worst reported severity if the patient reported one or more events. Adverse events with missing severity will be categorized as "Missing" for this summary.
- TEAEs potentially related to Study Drug by severity
- TEAEs leading to treatment discontinuation
- TEAEs leading to death
- Serious TEAEs
- Serious TEAEs potentially related to Study Drug
- TEAE with an incidence rate > 5% in any treatment groups
- Non-serious TEAE with an incidence rate > 5% in any treatment groups

Adverse event summaries will be presented alphabetically by SOC and preferred term (PT) and by descending frequency. An overview of AEs will be provided for all TEAes. AEs that lead to treatment discontinuation, and AEs that lead to death will be listed.

In addition, a summary of adjudicated AEs will be provided for pancreatitis and MACE separately. Adjudicated events will also be listed.

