4.10.4.2. Injection Site Reaction

Injection site reaction (ISR) is defined as any AE with PT or verbatim term containing 'Injection Site' that persisted for at least two days (i.e., event resolution date not on the day of the event onset date or the day after) or ongoing. ISR will be summarized using the MedDRA coding system, by PT and by treatment group.

Percentage of injections leading to ISRs will be summarized by PT and overall using the descriptive statistics.

Percentage of injections leading to ISR will be calculated as follows for each patient: (A/B)*100, where A = number of injections with an ISR, and B = total number of injections. Doses that are split across multiple injections are counted as a single injection.

The duration to resolution of an ISR will be summarized descriptively by treatment group and total ISIS 678354 treated. If there are multiple ISRs related to an injection and no overlap between ISRs, the duration will be calculated as the sum of the duration of all ISRs that are related to the injection. If there are overlaps, the duration will be calculated using the earliest start date and latest stop date of all ISRs that are related to the injection. For unresolved ISRs with missing stop date, the last participation date will be used in the calculation.

In addition, for patients who experienced ISR, time to onset of the first event, the number of injections prior to the first ISR will also be summarized descriptively by treatment group and total ISIS 678354 treated.

ISR will also be listed.

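### Splitting an adverse event at each severity change makes LCRIS definition (A) miss or under-grade injection-site reactions that worsen or change grade soon after the injection

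*Combined protocol and SAP*

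**What the plan says.** SAP 4.10.2 (Adverse Events) states that "if the severity of an AE changes during the study, a separate AE will be recorded for each severity on the AE CRF". It dates the chain so that the "AE start date of the second record will be the AE stop date of first record". It then says "These linked events should be compared pairwise", and the two cases that follow settle treatment-emergent status only. When both records fall after first dosing, "The worst AE is considered as a TEAE". Protocol 9.4.3.5 has a matching outcome for non-serious events: "Change in Severity (if applicable): AE severity changed".

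SAP 4.10.4.1 defines LCRIS in two parts.
- **Part (A)** covers "moderate or severe adverse events with the preferred terms (PTs) including Injection site erythema", swelling, pruritus or pain, with "event onset date on the day of injection and resolution date not on the day of injection or the day after injection", or still ongoing.
- **Part (B)** adds any injection-site AE, of any severity, that is the principal reason for stopping study drug.

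The section also plans summaries of moderate, severe and any LCRIS, the percentage of injections leading to LCRIS, duration, and time to onset.

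SAP 4.10.4.2 defines ISR more loosely. It takes any AE whose term contains the words Injection Site and which is ongoing or has its "event resolution date not on the day of the event onset date or the day after". There is no severity condition and no injection-day condition.

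Neither section says whether linked severity records are joined first. The sum and overlap rules in both sections govern duration, among events that already qualify.

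**The concern.** LCRIS (A) puts three conditions on a single AE: grade, onset on injection day, and persistence. The recording rule in 4.10.2 can spread these over two records of the same reaction. One record may then hold the right onset date and the other the right grade or length, so that neither qualifies.

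Grade changes are plausible. Protocol Appendix D grades erythema by diameter, 2.5–5 cm as mild and 5.1–10 cm as moderate, so redness that spreads past 5 cm changes grade and opens a new record.

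At stake is the SAP's dedicated summary of persistent moderate or severe local reactions: patient counts, percentage of injections, the moderate and severe split, and duration. Two programmers following this SAP could report different counts.

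**Working it through.** The plan gives no figure to reproduce. The check applies the stated rules to dated records.

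**Notation.** Injection day is Day 0. A record has a grade, a start day and a stop day, and record 2 starts on the day record 1 stops (SAP 4.10.2). The record's stop day is first taken as its resolution date.
- LCRIS (A), from 4.10.4.1: grade moderate or severe, start = 0, stop ≥ 2.
- ISR, from 4.10.4.2: stop − start ≥ 2.

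**Worked courses**

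| Course | LCRIS (A), record 1 | LCRIS (A), record 2 | ISR |
|---|---|---|---|
| Mild Day 0–1, moderate Day 1–6 | fails: mild | fails: starts Day 1 | counted (6 − 1 = 5) |
| Moderate Day 0–1, mild Day 1–6 | fails: stops Day 1 | fails: mild, starts Day 1 | counted (6 − 1 = 5) |
| Moderate Day 0–1, severe Day 1–6 | fails: stops Day 1 | fails: starts Day 1 | counted (6 − 1 = 5) |
| Mild Day 0–1, moderate Day 1–2, or the reverse | fails | fails | missed (1 and 1) |
| Moderate Day 0–3, severe Day 3–6 | counted, as moderate | fails: starts Day 3 | counted |
| Moderate Day 0–3, mild Day 3–10 | counted, duration ends Day 3 | fails: mild, starts Day 3 | counted |

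In the last row the duration rule does not recover the mild week, because it combines only events that are themselves LCRIS.

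Taken as one reaction (earliest start, latest stop, worst grade), every row starts on Day 0, reaches at least moderate and stops on Day 2 or later. Every row then meets both LCRIS (A) and ISR.

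**All single-change date patterns.** Let the grade change on day c = 0 to 13 and the reaction end on day r = c to 14. That gives 15 + 14 + … + 2 = 119 pairs. Three end before Day 2: (0,0), (0,1) and (1,1). The remaining 119 − 3 = 116 all meet LCRIS (A) and ISR as whole reactions. Record by record:

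- **Mild to moderate:** LCRIS (A) catches only c = 0, with r = 2 to 14, so 13 of 116.
- **Moderate to mild:** c = 0 and c = 1 are lost, 13 patterns each, so 116 − 26 = 90 of 116.
- **Moderate to severe, or severe to moderate:** c = 1 is lost, so 116 − 13 = 103 of 116.
- **ISR, in every case:** only c = 1 with r = 2 is lost, so 115 of 116.

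**The other reading of resolution date.** If it means the end of the whole reaction, persistence is met whenever r ≥ 2. The moderate-to-mild, moderate-to-severe and severe-to-moderate courses are then all caught (116 of 116). Mild to moderate stays at 13 of 116, because it fails on onset. The severe record in the fifth row still starts too late to count as severe. Duration still ends at the grade change, because the duration rule is written in start and stop dates.

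**The case against.** The strongest case against this has four parts.

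**The SAP does not say the definitions run record by record.** True: this is a step left unspecified, not a wrong method stated outright. But 4.10.2 defines what an AE record is, and nothing in 4.10.4.1 reassembles it. A programmer following the text would test records.

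**Resolution may not mean a record's stop date.** SAP 4.10.2 speaks of stop dates. Protocol 9.4.3.5 lists a severity change separately from recovery, and makes the change date a Resolution Date only for an event that became serious. This reading is open, and it rescues the fading course. It does not rescue the worsening course.

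**LCRIS is meant to be restrictive.** Requiring the moderate phase itself to persist is defensible, and a reaction that fully resolves within a day is excluded on purpose. That does not explain dropping a reaction that is moderate on Day 0–1 and severe to Day 6.

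**Other outputs show these reactions.** ISR catches nearly all multi-day reactions, the TEAE tables by worst severity have no onset or duration filter, and part (B) keeps reactions that lead to discontinuation. This stands and limits the harm.

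A reader might also infer more than the documents support:
- *That ISR is badly under-counted.* It is not, since it has no grade or injection-day condition.
- *That flu-like reactions are missed because only the worst record is kept.* SAP 4.10.4.3 is written for adverse events, not TEAEs, with no grade or duration condition on the record, so the first record meets the onset window.
- *That a number of missed patients can be derived from the Phase 2 rates of 12.2% and 4.2% in protocol 2.3.4.* Those reactions were predominantly mild, LCRIS (A) needs moderate or severe, and the documents give no share that change grade.

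**Conclusion.** The point holds for LCRIS (A). Under either reading of resolution date, a reaction that first becomes moderate or severe after injection day is missed (13 of 116 patterns caught), a moderate reaction that later becomes severe is graded moderate, and LCRIS duration stops at the grade change. If resolution date is the record's own stop date, a reaction that is moderate on injection day and changes grade by Day +1 can also be missed (90 or 103 of 116 caught, depending on the direction of change). ISR is affected only when every severity segment ends by the day after it began.

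This assumes that sites split records as 4.10.2 directs, that the definitions are applied to those records, and that reactions start on injection day and change grade once within the 14-day grid. The pattern counts weight all date combinations equally and are not expected patient frequencies. The number of patients affected, and any effect on the comparison between arms, cannot be derived from the documents.

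The consequence is an under-count and mis-grading in one descriptive local-tolerability summary. No efficacy conclusion depends on it. It should be corrected because the rules as written give a wrong count and the remedy is cheap.

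**What to change.** Add to SAP 4.10.4.1: before LCRIS (A) and its severity and duration summaries are applied, linked severity records for the same preferred term and the same injection are joined into one reaction, taking the earliest start, the latest stop and the worst severity. Apply the same joining before the persistence test in 4.10.4.2. If the SAP is not reopened, SAP section 1 allows the step as a deviation with its rationale documented in the clinical study report.

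The cost is a sentence in each section and one programming step, and 4.10.2 already describes how the records are linked. The downside is that LCRIS counts may rise slightly, because a reaction that is moderate only briefly would count if the whole reaction persists. If the sponsor intends the moderate phase itself to persist, the SAP should say so and state how reactions that worsen after injection day are counted.

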4.10.4.2. Injection Site Reaction

Injection site reaction (ISR) is defined as any AE with PT or verbatim term containing 'Injection Site' that persisted for at least two days (i.e., event resolution date not on the day of the event onset date or the day after) or ongoing. ISR will be summarized using the MedDRA coding system, by PT and by treatment group.

Percentage of injections leading to ISRs will be summarized by PT and overall using the descriptive statistics.

Percentage of injections leading to ISR will be calculated as follows for each patient: (A/B)*100, where A = number of injections with an ISR, and B = total number of injections. Doses that are split across multiple injections are counted as a single injection.

The duration to resolution of an ISR will be summarized descriptively by treatment group and total ISIS 678354 treated. If there are multiple ISRs related to an injection and no overlap between ISRs, the duration will be calculated as the sum of the duration of all ISRs that are related to the injection. If there are overlaps, the duration will be calculated using the earliest start date and latest stop date of all ISRs that are related to the injection. For unresolved ISRs with missing stop date, the last participation date will be used in the calculation.

In addition, for patients who experienced ISR, time to onset of the first event, the number of injections prior to the first ISR will also be summarized descriptively by treatment group and total ISIS 678354 treated.

ISR will also be listed.

4.10.4.3. Flu-like Reactions

Flu-like reactions (FLR) will be evaluated using the following 2 definitions:

Definition 1 (FLR 1): defined as adverse events with PTs including Influenza like illness, Pyrexia, Feeling hot, Body temperature increased, Chills, Myalgia, or Arthralgia, starting on the day of injection or next day.

ISIS 678354-CS3

Definition 2 (FLR 2): defined as adverse events with PTs including either (A) Influenza like illness or (B) Pyrexia or Feeling hot or Body temperature increased, plus at least two of the following symptoms with the PTs: Chills, Myalgia, or Arthralgia, starting on day of injection or the next day.

Flu-like reactions will also be summarized using the MedDRA coding system, by preferred term and by treatment group.

Percentage of injections leading to flu-like reactions will be summarized by treatment group using the descriptive statistics.

Percentage of the injections leading to flu-like reactions will be calculated as follows for each patient: (A/B)*100, where A = number of injections leading to flu-like reactions, and B = total number of injections.

For the subset of patients experiencing FLR(s), the time to onset of first FLR will be summarized using descriptive statistics.

Flu-like reactions will also be listed.

4.10.4.4. Bleeding TEAE

Bleeding TEAEs will be analyzed for the following categories. The number and percentage of patients experiencing events as well as the number of reported events, classified by SOC and PT, will be tabulated by treatment group. The risk different (95% CI) in the crude incidence rates between each active treatment group (or total ISIS 678354) and pooled placebo group will be provided.

- Bleeding TEAEs (defined based on the 'Haemorrhages' Standardized MedDRA Query [SMQ, both narrow and broad scope])
- Clinical bleeding TEAEs, i.e. bleeding TEAEs excluding events at the injection site and events related to a laboratory value
- Clinical bleeding events with concomitant anticoagulant or antiplatelet medication
- Clinical bleeding events without concomitant anticoagulant or antiplatelet medication

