4.10. Safety Evaluation

All safety summaries and analyses will be based upon the Safety Set as defined in Section 4.5.

Risk difference and corresponding 95% CI in the crude incidence rates between each active treatment group (or total ISIS 678354) and pooled placebo group in selected safety endpoint will be provided. The crude incidence rate (or percentage) is defined as the number of patients who experienced at least one event times 100 divided by the total number of patients. The 95% CI of risk difference in crude incidence rate will be estimated using the Miettinen-Nurminen (MN) method.

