For patients having eGFR \geq 25% decrease from baseline, the time to onset of the first event will be summarized using descriptive statistics.

Platelet Abnormalities:

The incidence of patients with post-baseline platelets results falling in each of the following categories will be summarized for the Safety Set and the subset of patients with normal baseline ($\geq 140,000/\text{mm}^3$). The risk different (95% CI) in the crude incidence rates between each active treatment group (or total ISIS 678354) and pooled placebo group will be provided for selected categories.

- Any 2 occurrences of platelet count < 140,000/mm³
- Any single occurrence of platelet count < 100,000/mm³
- Any 2 occurrences of platelet count < 140,000/mm³ or any single occurrence of platelet count < 100,000/mm³
- Worst platelet count falling in: ≥ 140,000/mm³, 100,000/mm³ to < 140,000/mm³, 75,000 to < 100,000/mm³, 50,000 to < 75,000/mm³, 25,000 to < 50,000/mm³, 0 to < 25,000/mm³ (the risk difference will not be provided for this category)
- Worst platelet reduction from Baseline $\geq 30\%$ and $\geq 50\%$

The incidence of patients with post-baseline platelets results falling in each of the following categories based on confirmed results will also be summarized:

- Worst platelet count falling in: ≥ 140,000/mm³, 100,000/mm³ to < 140,000/mm³, 75,000 to < 100,000/mm³, 50,000 to < 75,000/mm³, 25,000 to < 50,000/mm³, 0 to < 25,000/mm³ (the risk difference will not be provided for this category)
- Worst platelet reduction from Baseline $\ge 30\%$ and $\ge 50\%$

For patients having post-baseline platelet count $< 100,000/\text{mm}^3$, the time to onset of the first event will be summarized using descriptive statistics

ISIS 678354-CS3

The correlation between anti-platelet antibodies and platelet decrease as well as immunogenicity status may be explored if supported by data.

Hypersensitivity Related Analyte Abnormalities:

The number and percentage of patients falling in each abnormality category outlined below will be tabulated by treatment group. The risk different (95% CI) in the crude incidence rates between each active treatment group (or total ISIS 678354) and pooled placebo group will be provided for selected categories.

- Eosinophils > 650 cells/uL, > 1500 cells/uL, > 5000 cells/uL
- WBC > 10,800 cells/uL, > 13,000 cells/uL, > 15,000 cells/uL

Shift Analysis

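### Bleeding with and without anticoagulant or antiplatelet drugs is compared over all patients, so each row mixes bleeding risk with the arm's share of users

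*Combined protocol and SAP*

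**What the plan says.** SAP 4.10.4.4 lists four bleeding categories: all bleeding TEAEs, clinical bleeding TEAEs, "Clinical bleeding events with concomitant anticoagulant or antiplatelet medication", and "Clinical bleeding events without concomitant anticoagulant or antiplatelet medication". For the whole list it plans counts and percentages by treatment group, and a risk difference with 95% CI "in the crude incidence rates between each active treatment group (or total ISIS 678354) and pooled placebo group will be provided".

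The denominator is not in 4.10.4.4. It comes from SAP 4.10, where the crude incidence rate is the "number of patients who experienced at least one event times 100 divided by the total number of patients". The same section adds that "All safety summaries and analyses will be based upon the Safety Set as defined in Section 4.5", and that the interval "will be estimated using the Miettinen-Nurminen (MN) method". It mentions no stratification.

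Neither section gives a user or non-user denominator for the last two categories. Where the SAP wants a subset it says so: platelet abnormalities (SAP 4.10.5) are summarised for the Safety Set and for "the subset of patients with normal baseline", and the QTcF increase (SAP 4.10.7) is repeated in those with normal baseline QTcF. Without such wording, the general definition in 4.10 governs the bleeding rows.

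Section 4.10.4.4 also leaves open whether a bleed counts as *with* medication because of use at first dose, at onset of the bleed, or at any time in the study.

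**The concern.** Only someone taking an anticoagulant or antiplatelet drug can have a bleed *with* it. Over all patients, the with-medication percentage rises if users bleed more often, and it also rises if the arm simply contains more users. The without-medication percentage falls as the number of users rises. A risk difference on either row carries both components, and the reader cannot tell them apart from the row itself.

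Nothing in the design balances use. Protocol 5.1 permits stable oral anticoagulants, and protocol 4.2 stratifies only by pancreatitis history and previous volanesorsen. Use may also change after randomisation, because protocol 8.5.3 (Table 2) ties stopping these drugs to low platelet counts.

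The practical stake is interpretation. Platelets and bleeding are monitored closely in this trial. A split by these drugs invites the question of whether any excess bleeding is confined to patients already taking a drug that causes bleeding. With the planned denominator, the two rows do not isolate that.

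**Working it through.** The plan states no figure for bleeding by use of these drugs, so there is nothing to reproduce.

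**Inputs from the documents**
- Arm sizes: 22 (80 mg) + 21 (50 mg) = 43 active and 23 placebo, from the results summary at the front of the combined document.
- Phase 2 minor bleeding of 12.2% on active and 20.8% on placebo (protocol, Clinical Experience discussion). These are all-patient rates, used only to choose plausible non-user risks of 12% and 20%.

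**Assumed inputs** (not in the documents)
- Share of users, u: 10%, 20%, 30%.
- Bleeding risk among users, r: 20% to 50%.
- Bleeding risk among non-users, s: 12% to 20%.

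**Step 1: what each row measures.** Treat each patient's use as fixed. Then the with-row rate is u × r and the without-row rate is (1 − u) × s. With no drug effect, r and s are the same in both arms, so for active (A) minus placebo (P):
- with row: r × (uA − uP)
- without row: −s × (uA − uP)
- all clinical bleeding: (r − s) × (uA − uP)

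**Step 2: size for a 15-point excess of users on active.**
- With row: 0.20 × 15 = 3.0 points; 0.50 × 15 = 7.5 points.
- Without row: −0.12 × 15 = −1.8 points; −0.20 × 15 = −3.0 points.

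**Step 3: how often such an imbalance occurs.** Take independent binomial user counts, X out of 43 and Y out of 23, and compute P(|X/43 − Y/23| ≥ 0.15) exactly. The SD of the difference is √[u(1 − u)(1/43 + 1/23)].

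| u | SD (points) | P(imbalance ≥ 15 points) |
|---|---|---|
| 10% | 7.7 | 5% |
| 20% | 10.3 | 14% |
| 30% | 11.8 | 22% |

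Smaller imbalances are more common. With 4 to 20 users among the 66 patients, a difference of 10 points or more has a 12% to 40% chance for pooled active versus placebo. For 80 mg alone versus placebo, with users scaled to 45 patients, it is 23% to 53%.

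**Step 4: illustrations with no drug effect.**
- Users 8/43 vs 1/23, r = 30-50%, s = 12%: with row +4.3 to +7.1 points, without row −1.7.
- Users 2/43 vs 5/23, same risks: with row −5.1 to −8.5, without row +2.1.
- Users 7/43 vs 4/23 (nearly balanced): both rows within 0.6 points of zero.

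**Step 5: the two denominators side by side.** Suppose 12 vs 2 users, of whom 6 vs 1 bleed.
- As planned: 6/43 = 14.0% vs 1/23 = 4.3%, difference +9.6 points (Miettinen-Nurminen 95% CI −8.6 to 24.0).
- Among users: 6/12 = 50% vs 1/2 = 50%, difference 0.0 (95% CI −53.4 to 53.4).

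**Step 6: error rate.** With no drug effect, the Miettinen-Nurminen test of the with row, averaged over randomisation, rejects in 1.0% to 4.5% of trials (u = 10-30%, r = 30-50%), below the nominal 5%. Among trials with at least a 15-point excess of users on active, it rejects in 0.4% to 10.7%.

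**The case against.** The strongest reply is that this is ordinary chance imbalance. If study drug does not affect use, the expected difference in both rows over randomisation is zero, the test holds its level, and the planned interval already reflects the variation: +9.6 points with a CI from −8.6 to 24.0 would not persuade anyone of a drug effect. All of that stands. A reader might infer that the planned comparison is biased in general or produces false signals. The documents do not support that; the shift appears only in a trial whose user shares differ.

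Other parts of the reply also stand. SAP 4.10.4.4 states no purpose for the split, and a common denominator is normal when a total is simply broken down by context. The rows lie outside the testing hierarchy of SAP 4.9.1.3. The overall clinical bleeding row is shown beside them, and SAP 4.8 tabulates concomitant medication by arm and drug class, so an imbalance could be noticed. Among users the corrected interval may be nearly uninformative.

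A further objection limits the remedy. It is tempting to define users by any intake during the study and call the result unconfounded. It would not be: intake after randomisation can depend on platelet counts (protocol 8.5.3), so conditioning on it gives up the protection of randomisation that the all-patient comparison keeps.

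What the reply does not answer is that the printed difference cannot be read as a bleeding risk within users or non-users. A medication table elsewhere lets a reader suspect the problem but does not correct the row.

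**Conclusion.** The point holds as a minor one about how two descriptive rows are defined. Under SAP 4.10.4.4 read with 4.10, the with- and without-medication risk differences combine bleeding risk within users or non-users with each arm's share of users. In a given trial, a user imbalance shifts the two rows in opposite directions without any drug effect. For a 15-point imbalance the with row moves 3 to 7.5 points, if 20-50% of users bleed. An imbalance that large has a 5% to 22% chance at 43 vs 23 patients, if 10-30% are users. The user share and both risks are assumptions; the documents give none of them.

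It would go too far to conclude that type I error is inflated, that the primary or secondary conclusions are touched, or that a non-zero difference in these rows must be spurious. The calculations and the place of these rows in the plan support none of that.

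**What to change.** In SAP 4.10.4.4, for these two categories only:
- Define users and non-users by anticoagulant or antiplatelet use at first dose of study drug, with the medication dates handled as in SAP 4.8.
- Show the number of users and non-users in each arm.
- Use those numbers as denominators for the percentages and the Miettinen-Nurminen risk differences.
- If events classified by use at onset are still wanted, keep them as counts or a listing, and say that this is how they are classified.

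The cost is one derived flag from data already collected and a sentence or two in the SAP. Denominators will be small and intervals wide, especially among users. A patient who starts such a drug after first dose stays in the non-user group; that is the price of a grouping that study drug cannot influence.
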